1.0 BACKGROUND & RATIONALE

Scientific background and basis for hypothesis(es) to be tested. Include justification for conducting study and results of similar studies or pilot data.

Informal Caregivers of Cancer Survivors. Informal caregivers are people within the survivor's social network, related by blood or emotional attachment, who provide emotional, informational and/or instrumental support.⁵² The value of this unpaid labor force of 44 million caregivers in the United States⁵³ is estimated to be at least \$306 billion annually,^{54,55} with 5.7 million caregivers providing care to cancer survivors.⁵⁶ Caregivers of cancer patients become involved in complex care activities⁵⁷ for an average of 14 months.^{58,59} A shift to patient-centered care is facilitated by engaging the caregivers and requires the understanding of survivors' and caregivers' outcomes resulting from such engagement.^{60,61} Caregivers experience a range of psychological problems, disruption of daily routines, financial burdens, and role changes that accompany the care recipient's cancer diagnosis and treatment.⁶²⁻⁶⁴ Caring for the survivor often has negative consequences to the caregiver's family resources and health.^{65,66} Caregivers have poorer physical health than those in the general population, reflected by higher prevalence of arthritis, chronic back pain, and heart disease.⁶⁷ Between 30-50% of caregivers experience increased psychiatric morbidity, fatigue, sleep impairment.⁶⁸⁻⁷⁰ Psychological distress among caregivers is often present at levels equal to or greater than among cancer survivors.^{40,71-81} Risk of these morbidities is particularly high among caregivers who are female,⁸²⁻⁸⁴ less educated,⁸⁵ younger in age,⁸⁶ and who are caring for younger adult survivors.^{87,88} These findings explain increased use of health care services among caregivers of those recently diagnosed with cancer.^{89,90}

Meaningful involvement in the survivor's care may also have a positive impact on caregivers' health,⁹¹⁻⁹⁴ which improves the quality of care they provide to the survivors.⁹⁵⁻⁹⁸ For these reasons, interventions providing caregivers with tools such as the SMSH are highly valuable.^{99,100} Further, psychosocial interventions that directly improve caregivers' health,¹⁰¹ reduce psychological distress and address problem-solving and communication skills,¹⁰² are also potentially beneficial to survivors and their caregivers. The proposed research will deliver psychosocial (TIP-C) and educational (SMSH) interventions and test their optimal sequencing for survivors with known levels of distress and symptom severity as well as their impact on their caregivers who often experience distress and associated other symptoms (e.g., poor sleep, fatigue).

Symptom burden in cancer survivors. Physical and psychological symptoms are aggravated while cancer survivors are in treatment.^{103,104} Survivors' symptom burden¹⁰⁵⁻¹¹² is often the primary reason for altering or stopping chemotherapy^{113,114} leading to suboptimal treatment at the very least,¹¹⁵⁻¹¹⁷ and life threatening recurrence or metastasis at the extreme.^{118,119} The prevalence of specific symptoms (e.g., fatigue, pain, depression, anxiety, disturbed sleep, nausea and vomiting, neuropathy)¹²⁰⁻¹²⁵ varies by cancer diagnosis, treatment type, gender, ethnicity and age,^{98,99} variables that will be empirically tested as potential tailoring factors in decision rules that will be formulated in this research. The number of symptoms reported by cancer survivors can be as high as 14.^{126,127} Approximately 30% of cancer survivors report psychological distress (depression and anxiety). Major depression occurs in approximately 16%, and subthreshold depressive disorders occur in 22% of cancer survivors during treatment.²⁸ These prevalence rates are about 3 times higher than in the general population. Even when depression and anxiety do not meet threshold for clinical diagnoses, these symptoms are still associated with significant health impairments, yet are highly treatable,^{128,129} and will be in this trial, potentially saving healthcare costs and improving outcomes. Further, in our past studies, Latinas with breast cancer reported a higher number and more symptom burden/distress than did non-Hispanic white women with similar diagnoses.³¹ Therefore, we will enroll an ethnically diverse sample (includes 30% Hispanic/Latino participants) in this trial to address a significant symptom management need. Given the increasing population of Hispanic cancer survivors, providing and testing an intervention in the participant's primary language could have national significance. A series of longitudinal studies¹³⁰⁻¹³³ including those conducted by this team^{130,131}, found an association between increasing symptom prevalence and poorer physical and emotional functioning. Our team's past work¹³⁴ and that of others¹³⁵ documented the associations between reductions in symptoms and lower number of hospitalizations, office and ED visits.¹⁰ The proposed interventions are significant because they will address the multiple symptoms experienced by survivors during treatment and the associated health care service use.

2.0 OBJECTIVE(S)/SPECIFIC AIMS

Purpose and specific aims of the study.

Informal caregivers, typically family members or friends, provide more than half of the care needed for the 5.7 million cancer survivors in the United States, often with negative health consequences. At least 30% of survivors and their caregivers report psychological distress (depression and anxiety) and such distress may interfere with optimal symptom management. This study will support both members of the survivor-caregiver dyad in the management of the survivor's cancer- and treatment-related symptoms and the dyad's psychological distress.

Design: We will use the sequential multiple assignment randomized trial (SMART) design, a newer adaptive design. The SMART moves beyond a traditional RCT to a precision approach to determine the right treatment at the right dose with the right sequence for the right survivor-caregiver dyad. We will use two evidence-based interventions: Symptom Management and Survivorship Handbook (SMSH) and Telephone Interpersonal Counseling (TIP-C). While we have established the overall efficacy of these interventions, but individuals differ in responses. When an intervention does not initially work, clinic logic is to either extend the timeframe or prescribe a different intervention. Yet, such alternatives are seldom tested nor evidence-based. However, they will be in this study.

Sample: We will enroll 298 survivors with elevated depression or anxiety who are undergoing chemotherapy or targeted therapy for a solid tumor and their 298 caregivers.

Procedure: Dyads will be initially randomized to SMSH alone or TIP-C +SMSH. If the survivor's elevated depression or anxiety does not respond to SMSH alone by week 4, dyads will be re-randomized to continue with SMSH to give it more time or to TIP-C+SMSH. Outcome data will be collected at baseline, weeks 13 (post-intervention) and 17 (follow-up). Assessments during weeks 1-12 will document changes in symptoms, intervention receipt, enactment and fidelity.

Specific aims: **1)** Determine if dyads in the TIP-C+SMSH as compared to the SMSH alone group created by the first randomization will have: a) lower depression, anxiety, and summed severity of 13 other symptoms at weeks 1-12, 13, and 17 (primary outcomes); b) lower use of healthcare services (hospitalizations, urgent care or emergency department [ED] visits) during 17 weeks (secondary outcomes); c) greater self-efficacy, social support, and lower caregiver burden during weeks 13 and 17 (potential mediators). **2)** Among nonresponders to the SMSH alone after 4 weeks, determine if dyads assigned to TIP-C+SMSH as compared to the SMSH alone group created by the second randomization will have better primary and secondary outcomes and potential mediators at weeks 5-12, 13, and 17. **3)** Test the interdependence in survivor's and caregiver's primary and secondary outcomes. **4)** Determine which characteristics of the dyad are associated with responses to the SMSH alone during weeks 1-4 and optimal outcomes for the dyad during weeks 1-12, 13 and 17 so as to determine tailoring variables for the decision rules of individualized sequencing of interventions. Findings will be used to improve symptom management and reduce distress in survivor-caregiver dyads.

3.0 SAMPLE ELIGIBILITY CRITERIA

Specific inclusion/exclusion requirements which must be met for entry.

Inclusion criteria for the survivors are: **1)** age 18 or older; **2)** undergoing chemotherapy, hormonal therapy, or targeted therapy for a solid tumor cancer; **3)** able to perform basic activities of daily living; **4)** cognitively oriented to time, place, and person (*determined by recruiter*); **5)** reporting severity of >2 on depression or >4 on anxiety using a 0-10 standardized scale; **6)** able to speak and understand English or Spanish; **7)** access to a telephone and **8)** has a caregiver who can be in any relationship role (e.g., spouse, sibling, parent, friend) who can participate with them.

Exclusion criteria are: **1)** diagnosis of a psychotic disorder in the health record; **2)** nursing home resident; **3)** bedridden; **4)** currently receiving counseling and/or psychotherapy. Inclusion criteria for the caregivers are: **1)**

age 18 or older; **2)** able to speak and understand English or Spanish; **3)** access to a telephone; **4)** not currently receiving counseling and/or psychotherapy; and **5)** not currently treated for cancer.

The advantages of these inclusion criteria are in study generalizability. Solid tumors have been selected because cancer- and treatment-related symptoms can be effectively managed in this population with the two interventions (see section C2). Site of cancer and other prognostic factors will be controlled in randomization (see C7). Thus, groups compared in study hypotheses will be balanced on disease and treatment characteristics. The cut-offs of >2 on depression and >4 on anxiety indicate their presence at moderate or severe levels based on established interference-based cut-points.²²⁴ The need to screen on depression and anxiety is premised on a meta-analysis that psychosocial interventions are most beneficial for those with elevated distress.^{225,226} By allowing survivors to select their own caregivers, findings would be generalizable to the cancer survivor population who may be single or rely on other people for support. The exclusion of caregivers currently treated for cancer will preserve the distinguishability of the “survivor” and “caregiver” roles within the dyad. Our prior research indicates that participation in counseling and/or psychotherapy for either dyad member is rare during survivors’ treatment. These exclusion criteria will not substantially limit the population but will eliminate potential confounding of the intervention effects with extraneous influences.

4.0 PARTICIPANT RECRUITMENT/ENROLLMENT

Describe how study participants are to be recruited and enrolled in the study with appropriate contact phone numbers, etc. Stratification factors, participant characteristics which are balanced across treatment arms or used to determine intervention doses are described here. The randomization scheme is included here if applicable.

Sample. We will recruit 298 dyads (see below for power), allowing for 22% attrition, for a final post-attrition sample of 232 dyads available for analysis. Based on the demographic characteristics of the AZ population, the sample will consist of approximately 60% non-Hispanic white, 30% Hispanic/Latino, 3% each African American and Asian American, and 4% American Indian participants. There is an ample pool of cancer survivors available to meet enrollment targets. Of the estimated 35,810 newly diagnosed cases of cancer²²⁷ in AZ in 2017, the majority were solid tumors. Conservatively, we will have easy access to about 3000 survivors with our existing sites, of which approximately one third (n=1000) should satisfy the inclusion criteria. Following the initial recruitment contact, we anticipate about 10% will consent to participate, thus we can recruit 100 dyads per year. Given this team’s past successful recruitment at the UACC and community sites (letters of support), the proposed study will easily meet the recruitment goal of 99 dyads each year of the 3 years of recruitment.

Sample size and power considerations. To determine sample size, we started at the right of the schematic in Figure 1 (the second randomization) and moved from right to left to determine the needed number of consenting dyads. To power the comparisons on primary outcomes for the groups created by the second randomization (Aim 2), we used the effect size of Cohen’s $d=0.39$ (adjusted for baseline), the smallest seen in the preliminary data for TIP-C against an educational intervention (Table 1) to conservatively estimate sample size requirements. We further adjusted this effect size for the reduction in error variance due to 10 repeated measures of primary outcomes. In past studies, Pearson correlation coefficients between pairs of repeated measures of depression, anxiety and summed severity of other symptoms ranged from $r=0.36$ to 0.77, resulting in the range of the adjusted effect sizes from $d=0.54$ to 0.84. Using the smallest adjusted $d=0.54$, the required sample size is 60 per group created by the second randomization, for power of .80 or greater in two-tailed tests at the 0.05 level of significance.

Moving from left to right in Figure 1 (schematic), 120 dyads from two groups created by the second randomization will be non-responders to the SMSH alone. From past work, response rate to the SMSH on depression and anxiety was approximately 30%,²²⁸ therefore 120 non-responders will be 70% of 172 randomized to the SMSH alone in the first randomization. The comparison of these 172 to 60 dyads allocated to the TIP-C+SMSH in the first randomization will have power of 0.95 to detect the effect size of 0.54 (adjusted for the repeated measures) in testing the hypothesis associated with Aim 1. The tests of mediation and interdependence effects in Aim 3 will have an even greater power because of further reduction in error variance. Aim 4 is exploratory, thus formal power considerations are not applicable. In summary, the total

required post-attrition sample size for all specific aims is N=232. To account for 22% attrition based on past work, we will need 298 dyads to consent.

Recruitment and retention of participants.

Accrual. Recruiters have research roles and do not provide direct care at the sites. They will approach survivors during clinic visits and explain the study. Survivors can choose to consent at that time or take the packet home to discuss with their caregivers. Recruiters will follow up during a clinic visit or by phone to further explain the study, answer questions, and discuss the study with caregivers. If the survivor or caregiver give verbal consent over the phone, the participant will return the signed consent forms with witnessed signature in a postage paid envelope. If the consent forms are not returned within one week, the recruiter will call the participant to ask that the signed consent forms be mailed if they wish to participate.

Recruiter training. The study Coordinator will conduct recruiter training that includes didactic information, role-playing, and return demonstration of recruiting per script. Recruiters will introduce the study to survivors: 17-week study duration, randomizations to TIP-C+SMSH versus SMSH alone to help manage symptoms, 12 weekly calls and three interviews, no cost to study participation, risks/benefits, and incentives.

Subject incentives. We will provide gift cards for completing baseline, 13 and 17-week assessments.

Incentive payments not only significantly improve recruitment rates²²⁹, but there are no significant differences in key dependent variables for those offered versus those not offered an incentive.²³⁰ Provision of incentives equivalent to the demands of participation is vital to successfully recruiting minorities into research and getting a culturally representative diverse sample.²³¹⁻²³⁴ After every assessment, participants will receive thank you letters and gift cards from a large retail merchant in graduated amounts (\$40 after 1st, \$50 after 2nd and \$60 after 3rd). The total compensation will be \$150 for about 6-10 hours of participants' time over 17 weeks.

Strategies to minimize attrition. 1) Recruiters will emphasize the importance of participating in the entire intervention each week. 2) Survivors and caregivers will be asked to mark their calendars for study calls. 3) email or text reminders about upcoming telephone contacts will be sent if agreed to by participants. 4) Weekly calls will maintain contact with all participants for the entire study duration. 5) Graduated compensation for assessments will be provided. These strategies have worked well in the past. Participants will be assured of the confidentiality of all information and that refusing to participate will not alter their care. Survivors will continue to receive standard medical and nursing care and may seek care from their health providers for any health problems that arise. For dyads that refuse to participate, the recruiter will seek consent to collect their de-identified demographic data and ask about the reason for refusal. These data help us understand who declines and contribute to external validity and generalizability of the findings.

Community ties and cultural sensitivity. We use experienced staff members with extensive ties to the local survivorship communities. The study brochures will be developed in English and in Spanish with community advisors.^{31,210} Seven principles of language competence, cultural competence, ethical conduct, mission or purpose, empathy, graciousness and credibility²³⁵ will be incorporated in all interactions. We will show cultural sensitivity along two dimensions.^{236,237} Surface structure involves matching messages to observable 'superficial' characteristics of the target population (e.g., speaking English or Spanish). Deep structures involve incorporating some of the socio-cultural, historical, environmental and psychological forces that influence health behaviors. For example, we will incorporate the value of *personalismo* by talking about participants' lives at the beginning of sessions. Participants from past studies have appreciated the flexibility and respect (*respeto*) inherent in our caregiver definition, which allowed survivors to choose the person to participate.²³⁸ These techniques allow us to personalize our interactions, addressing both personal and cancer issues of concern. This approach is critical to gain trust (*confianza*).

Randomization. Following the baseline interview, dyads will be randomized to either SMSH alone (N=172 post-attrition) or to TIP-C+SMSH (N=60 post-attrition). A minimization algorithm will be programmed by [name] to balance arms by recruitment location, site of cancer, stage of cancer (early versus late), type of treatment, and survivor's relationship to the caregiver (spouse vs non-spouse).²³⁹ The second randomization will occur for those who do not respond to the SMSH alone after the first 4 weeks using the same approach as the first randomization except in 1:1 ratio. The study coordinator will run the computer algorithm from the main study office (Tucson) to ensure allocation, concealment, and blinding.

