Aim 1, Hypothesis 1: Dyads initially randomized to the TIP-C+SMSH will report lower depression, anxiety, and summed severity of other symptoms at weeks 1-12, 13, and 17, and lower unscheduled health services use, higher self-efficacy and social support, and lower caregiver burden at weeks 13 and 17 as compared to those initially randomized to the SMSH alone. This hypothesis will be tested using statistical model #1 that relates repeated measures of the survivor or caregiver outcome y (one at a time) to the group assignment variable xx_1 , outcome at baseline xx_2 , time entered as a class variable to model potentially non-linear patterns, and other covariates. For normally distributed outcomes, this model will be fit as a linear mixed effects model (LME). Generalized linear mixed effects (GLME) modeling will be used if outcome is not normally distributed and cannot be normalized using transformations. For health service use, statistical model #1 will be implemented as a GLME model with Poisson distributed errors, or as a zero-inflated Poisson or negative Binomial model based on the distribution of the counts of different health services uses. Each type of health services use (e.g., hospitalizations, ED visits) will be analyzed separately. The explanatory variables including study group will be evaluated as predictors of zero inflation (whether or not the count is zero), and also as predictors of the magnitude of the count when it is not zero. The main effects of the group variable xx_1 will be tested.

Aim 2, Hypothesis 2: Dyads where survivors do not respond to the SMSH alone during weeks 1-4 and have TIP-C added during weeks 5-12, will report lower depression, anxiety, and summed severity of other symptoms at weeks 5-12, 13, and 17, and lower unscheduled health services use, higher self-efficacy and social support, and lower caregiver burden at weeks 13 and 17 as compared to those who are re-randomized to continue with the SMSH alone. The strategy described under the analyses for Aim 1 will be implemented for the repeated outcome measures during weeks 5-12 and weeks 13 and 17 that will be related to group assignment from the second randomization, symptom severity during week 4, time, and covariates.

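### The Aim 1 power of 0.95 uses an undiluted d of 0.54, although about 35% of the comparator dyads have TIP-C added from week 5

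*Combined protocol and SAP*

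**What the plan says.** Section 4.0, Sample size and power considerations, starts from d=0.39, "the smallest seen in the preliminary data for TIP-C against an educational intervention". It raises this to a range of 0.54 to 0.84 for repeated measures and takes the low end. With d=0.54, "the required sample size is 60 per group created by the second randomization", which is the Aim 2 comparison. The first-stage arm is then built backwards: "120 non-responders will be 70% of 172 randomized to the SMSH alone in the first randomization". The Aim 1 comparison of these 172 dyads with 60 on TIP-C+SMSH "will have power of 0.95 to detect the effect size of 0.54 (adjusted for the repeated measures").

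Section 4.0, Randomization, re-randomises non-responders "using the same approach as the first randomization except in 1:1 ratio". Section 5.0 (Aim 2, Hypothesis 2) gives the timing: "Dyads where survivors do not respond to the SMSH alone during weeks 1-4 and have TIP-C added during weeks 5-12".

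For Aim 1, section 2.0 compares TIP-C+SMSH dyads "as compared to the SMSH alone group created by the first randomization will have" lower symptoms over weeks 1-12, 13 and 17. Section 5.0, repeated in 8.0, makes the analysis intent to treat and says "The main effects of the group variable xx_1 will be tested". Nothing in the documents discounts, censors or reweights the stepped-up dyads in Aim 1.

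**The concern.** The TIP-C group of Aim 2 sits inside the comparator of Aim 1. The plan assumes that adding TIP-C to non-responders is worth d=0.54. If so, a third of the Aim 1 comparator gains that benefit from about week 5, and the difference between the two first-stage groups must fall below 0.54 from then on. The plan cannot assume 0.54 for the step-up and also assume an undiminished 0.54 for Aim 1.

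What is at stake is interpretation. Aim 1 covers the primary outcomes. A reader who meets a null Aim 1 result and a stated power of 0.95 would conclude that starting with TIP-C adds little. Yet the better stepped-up TIP-C works, the smaller the Aim 1 difference becomes. The first-stage contrast itself is legitimate and is unbiased for its own estimand; only the power figure attached to it is in question.

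**Working it through.** **Inputs.** From section 4.0: n=60 and n=172 after attrition, d=0.54, 120 non-responders, 1:1 second randomization. Two-sided alpha of 0.05 is stated for Aim 2 and assumed to carry over. From sections 2.0 and 5.0: 14 occasions (weeks 1-12, 13, 17), 10 of them at week 5 or later. Not in the documents: *e*, the step-up effect as a share of the initial TIP-C effect.

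**The plan's own figure.** Noncentral t on 230 df. Noncentrality = 0.54 / √(1/60 + 1/172) = 0.54 / 0.1499 = 3.60. Power = 0.948 (0.950 by the normal approximation). The stated 0.95 is reproduced.

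**Stepped-up share.** 120/2 = 60 dyads; f = 60/172 = 0.349.

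**Diluted contrast, equal occasion weights, immediate step-up effect.** d(e) = 0.54 × (1 − f·e·k/14). Here k=10 if week 5 counts as diluted. k=9 if it does not, because section 7.0 puts the symptom assessment before the counselling part of the call. For e=1 and k=10: 1 − 0.349 × 10/14 = 0.751, so d = 0.405.

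| e | d, k=10 | power, k=10 | d, k=9 | power, k=9 |
|---|---|---|---|---|
| 1 | 0.405 | 0.768 | 0.419 | 0.795 |
| 0.75 | 0.439 | 0.831 | 0.449 | 0.847 |
| 0.50 | 0.473 | 0.881 | 0.480 | 0.890 |
| 0.25 | 0.506 | 0.920 | 0.510 | 0.923 |
| 0 | 0.540 | 0.948 | 0.540 | 0.948 |

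Even power of 0.94 needs e of at most 0.080 (k=10) or 0.089 (k=9).

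**Sensitivity at e=1.**

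- *Unequal occasion weights.* Generalised least squares weights, with correlation 0.36 + 0.41·ρ^(lag−1), fall from 0.77 towards 0.36, the range in section 4.0. For ρ from 0.5 to 0.95, power is 0.77-0.80 (week 5 diluted) or 0.79-0.81 (undiluted).
- *Slow build of the step-up effect only*, linear over 8 sessions. The step-up shares sum to 4.5 + 2 = 6.5 of 14 if rated after the session, or 3.5 + 2 = 5.5 if rated before. d = 0.453 or 0.466; power 0.85 or 0.87.
- *Slow build at both stages*, with 0.54 as the first-stage average. Factor = 1 − f × 6.5/10.5 = 0.784, or 1 − f × 5.5/9.5 = 0.798. Power 0.80 or 0.82.
- *Larger undiluted effect, k=10.* Power is 0.90 at d=0.65 and 0.99 at d=0.84. To reach 0.95, the undiluted d must be about 0.72 (0.70 with k=9).

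**The case against.** The strongest reply is that the sentence is true as a conditional statement: if the Aim 1 contrast is 0.54, power is 0.95. That is correct, but the section offers the figure as the power for testing the Aim 1 hypothesis, with an effect size taken from undiluted TIP-C, and gives no sign that the expected contrast is smaller.

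A second reply is that little follows. Aim 2 drives the sample size, 0.54 is the low end of 0.54 to 0.84, the only stated target is 0.80, and an eight-session course is unlikely to work fully in its first week. This holds in part. The 0.77-0.79 result is the full-and-immediate end of the range, and the slower or partial cases give 0.80 to 0.92. But a full step-up effect is what the plan itself assumes for Aim 2, and at d=0.54 no full-effect case shown reaches 0.90.

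A third reply is that the replacement figures rest on inputs the documents do not give. That stands, which is why a range with stated assumptions is needed. Nor is 0.77 a floor:

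- Initial TIP-C ends after week 8. Suppose its effect then falls to 75% (an assumption), the stepped-up effect stays at its full level, and 0.54 remains the initial arm's average. The factor is 1 − 0.349 × 10/12.5 = 0.721, d = 0.389 and power about 0.73.
- The PROMIS depression and anxiety forms have follow-up only at weeks 13 and 17, both after step-up. Full dilution there gives d = 0.54 × (1 − 0.349) = 0.352 and power about 0.65.
- With the group sizes held, a stepped-up share of 25% gives 0.84 and one of 40% gives 0.73.

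Finally, a careful reader can already work out the comparator from the design text. That is fair, so the clause describing the comparator is optional.

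**Conclusion.** The concern holds. The 0.95 is correct arithmetic for a contrast that Aim 1 will not have if the plan's own Aim 2 assumption is true. With d=0.54 as given, equal weight on 14 occasions and an immediate step-up effect, power is about 0.77-0.79 at full effect, 0.83-0.85 at 75%, 0.88-0.89 at 50% and 0.92 at 25%. At full effect the type II risk is therefore about 21-23% instead of 5%. Power close to 0.95 requires essentially no step-up effect, or an undiluted effect of about 0.70-0.72.

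That dilution is missing from the power statement is certain from the documents. Its size depends on the step-up effect, how fast it builds, the occasion weights and the actual share of non-responders. How 0.54 was derived from 0.39 was not examined here. Type I error, the validity of the Aim 1 test and the sample size are not affected.

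**What to change.** In section 4.0, Sample size and power considerations, replace the sentence giving 0.95 with wording such as:

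> Power is 0.95 for a contrast of d=0.54. About 60 of the 172 dyads will have TIP-C added from week 5, so the expected Aim 1 contrast is smaller. Averaging equally over 14 occasions, power is about 0.77-0.79 if stepped-up TIP-C has the full effect at once, and about 0.83, 0.88 and 0.92 if it has 75%, 50% and 25% of it. These figures assume equal occasion weights and an immediate step-up effect; the full-effect figure also assumes the same effect at both stages.

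Optionally, in section 2.0 and in Hypothesis 1 of sections 5.0 and 8.0, add a clause describing the comparator as SMSH first, with half of the non-responders stepped up to TIP-C from week 5. The result is then less likely to be read as a comparison with SMSH alone throughout.

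The cost is wording only: no extra dyads, data or analyses, and no change to the hypothesis or test. The stated Aim 1 power becomes less favourable, about 0.77 to 0.92 depending on the step-up effect instead of a single 0.95.
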